Précis:	EROCA is a prospective, randomized, open-label, clinical endpoint study comparing standard prehospital care to expedited transport of patients with refractory out-of-hospital cardiac arrest (OHCA) to a qualified emergency department capable of performing advanced resuscitation including extracorporeal cardiopulmonary resuscitation (ECPR). A maximum total of 30 patients will be randomized in the prehospital setting. The primary objectives are to determine the proportion of qualifying OHCA patients arriving to a qualified ED within 30 minutes of the initial 911 call and what proportion of patients can have ECPR initiated within 30 minutes of ED arrival. Patients arriving at the qualified ED will be treated under a standard institutional guideline and will be followed in the hospital for adverse events. In addition, patients will have follow up visits at 90 days to determine functional and neuro-cognitive outcomes.
Objectives:	
Co-Primary: Determine what proportion of patients with refractory OHCA can be reliably delivered to an ECPR-capable ED within 30 min of either the 911 call or prehospital provider witnessed first cardiac arrest (qualifying OHCA event).
 
Co-Primary: Determine what proportion of patients with ongoing refractory cardiac arrest that have ECPR initiated within 30 minutes of ED arrival.
 
Safety: To estimate frequency of adverse events associated with study interventions.
 
Exploratory: Demonstrate the feasibility of field randomization of patients with refractory OHCA based on estimated time from 911 call or EMS witnessed arrest to qualified ED arrival
 
Exploratory: To provide preliminary estimates regarding neurological outcomes following this treatment.

Endpoints	
Co-Primary : Time interval from 911 call or prehospital provider witnessed first cardiac arrest to qualified ED arrival in minutes
 
Co-Primary : Time interval from qualified ED arrival to ECPR initiation in minutes
 
Safety: Composite of major hemorrhage (requiring transfusion of over 4 units packed red blood cells per incident), arterial thrombosis (stroke, renal infarction, limb ischemia), venous thrombosis (pulmonary embolism or deep venous thrombosis), hemopericardium (requiring pericardiocentesis), pneumothorax(requiring thoracostomy tube placement), or vascular injury (causing complete occlusion and/or requiring vascular

	procedure).
	Exploratory: Utility weighted modified Rankin Scale at 90 days
	Exploratory: Neuropsychological and cognitive testing using NIH toolbox
	Exploratory: Time to vascular access and time to ECPR cannulation
Population:	Out-of-hospital cardiac arrest patients who do not have return of spontaneous circulation after initial rhythm analysis by first- responders who can potentially arrive at a qualified ED in persistent cardiac arrest within 30 minutes of initial 911 call or EMS witnessed first cardiac arrest.
Phase:	2
Number of Sites	
enrolling participants:	1
Description of Study Interventions :	Patients in the field will be randomized to either early transport to the hospital versus standard care (continued attempts at advanced cardiac life support in the field). Standard clinical procedures in the hospital will be followed for refractory cardiac arrest patients.
Study Duration:	30 months
Participant Duration:	Three months

SCHEMATIC OF STUDY DESIGN

EMS = emergency medical services, CPR = cardiopulmonary resuscitation, mCPR = mechanical CPR, eCPR = extracorporeal CPR, ACLS = advanced cardiac life support, ROSC = return of spontaneous circulation, TOR = termination of resuscitation, SR = shockable rhythms, ED = emergency department, UM = University of Michigan

2 INTRODUCTION: BACKGROUND INFORMATION AND SCIENTIFIC RATIONALE

2.1 BACKGROUND INFORMATION

2.1.1 CLINICAL SIGNIFICANCE

[figure not shown]
Approximately 200,000 people are treated for out-of-hospital cardiac arrest (OHCA) each year in the United States. The modest improvement in survival rates over the past decade have been primarily attributed to better implementation of cardiopulmonary resuscitation (CPR), advanced cardiac life support (ACLS), and post-cardiac arrest care. However, no new therapies have been proven effective in more than a decade. The result is a plateauing of overall survival rates at approximately 10% [Mozaffarian 2015]. Extracorporeal cardiopulmonary resuscitation (ECPR) using percutaneous veno-arterial extracorporeal circulation (VA-ECMO) is emerging as a feasible and potentially effective resuscitation strategy for non-traumatic OHCA patients who fail standard therapy. In published case series, survival rates range from 4-33%, and organ donation as a secondary outcome occurs in 5-15% of patients. Despite the promise of this emerging therapy, a fundamental barrier to widespread implementation is the fact that efficacy of ECPR for OHCA has yet to be proven in a prospective randomized clinical trial. In October of 2015, the International Liaison Committee on Resuscitation (ILCOR) Consensus on Science and Treatment Recommendation made the following treatment recommendation: *We suggest ECPR is a reasonable rescue therapy for selected patients with cardiac arrest when initial conventional CPR is failing in settings where this can be implemented (weak recommendation, very-low-quality evidence)* [Callaway 2015]. The primary knowledge gap listed was: *Controlled clinical trials are needed to assess the effect of ECPR versus traditional CPR on clinical outcomes in patients with cardiac arrest.* The new AHA guidelines for CPR and Emergency Cardiovascular Care published in October 2015 state: *There is insufficient evidence to recommend the routine use of ECPR for patients with cardiac arrest. In settings where it can be rapidly implemented, ECPR may be considered for select cardiac arrest patients for whom the suspected etiology of the cardiac arrest is potentially reversible during a limited period of*

mechanical cardiorespiratory support (Class IIb, LOE C-LD) [Link 2015]. Thus, the most recent consensus of the world's experts in the field is a call for more evidence in the form of a prospective randomized clinical trial.

2.1.2 RELEVANT CLINICAL RESEARCH

Almost all published case series of successful ECPR for OHCA initiate ECPR in the emergency department [Chen 2008, Kagawa 2010, Nagao 2000 and 2010, LeGuen 2011, Morimura 2011, Avali 2012, Bellezzo 2012, Johnson 2014, Sakamoto 2014, Stub 2014]. The reason for this strategy is that the shorter the interval from cardiac arrest onset to initiation of ECPR, the better the chance for a favorable outcome. Figure 3 illustrates this relationship in recent OHCA studies (published after 2010) that specifically reported the collapse to ECPR interval and survival with good neurologic function for the entire study population. These and similar reports are the basis for our initial targeting of a 911 call to ECPR interval <60 min in the EROCA trial. In many countries where ECPR is used to treat OHCA, the ED is routinely staffed by physician specialists in anesthesia or cardiology with more formal training and experience in ECMO than emergency medicine physicians in the U.S. Institutions in the U.S. that perform ECPR for OHCA typically rely on cardiac surgery or cardiology consultants to come to the ED to place ECMO catheters and initiate ECPR [Johnson 2014]. However, the model has many logistical limitations that make it challenging to initiate ECPR within the therapeutic window, and if maintained will be a persistent barrier to widespread implementation.

One example of a program that has incorporated emergency medicine physicians into the ECPR team that includes cardiologist and cardiothoracic surgeons Sharp Memorial Hospital in San Diego [Bellezzo 2012]. In their published case series, 8 out of 18 OHCA patients that met inclusion/exclusion had ECPR successfully initiated in the ED, and 3/18 had spontaneous ROSC before ECPR could be initiation. Of the 8 patients successfully treated with ECPR, 5 survived with good neurologic function (63%). However ECPR catheters could not be placed in 4 patients, and two other patients were reported to have fatal complications of catheter placement (aortic dissection and bifemoral vein cannulation). Although these results demonstrate feasibility in a US ED, they also emphasize the importance of validated training and maintenance of competency for both clinical trial participation and widespread implementation.

Relationship between collapse to ECPR interval and survival with good neurologic function in refractory OHCA cardiac arrest 1) Maekawa 2013; 2) Kagawa 2012; 3) Fagnoul 2013; 4) Haneya 2012; 5) Nagao 2010; 6) Avali 2012; 7) Le Guen 2011. Diamonds represent median intervals from collapse to ECPR and lines represents range. (Adapted from Fagnoul 2014 table 2.)

2.2 RATIONALE

Currently available evidence suggests that ECPR for OHCA should be initiated within 60 minutes of cardiac arrest onset to maximize the potential therapeutic benefit. Therefore, in addition to delivering patients to the ED within 30 minutes, it is essential that our system of care is able to initiate ECPR within ≤ 30 minutes of ED arrival. In a recently published study of ED-initiated ECPR, the median time from ECPR team arrival to initiation of ECPR was 20 minutes [IQR 15-30 minutes] [Stub 2014]. The goal is to achieve < 30 -minute arrival to cannulation for all patients meeting inclusion/exclusion criteria for ECPR therapy.

2.3 POTENTIAL RISKS AND BENEFITS

2.3.1 KNOWN POTENTIAL RISKS

Risks of mechanical or traditional CPR: bruising and soreness of the chest is common after mechanical or traditional CPR. Pneumothorax and hemo-pericardium are also possible risks. Rib fractures and solid organ injuries (liver and spleen) are additional potential risks.

Risk of EMS (early transport): motor vehicle crash during transport to the hospital.

Alternatives to early transport with mechanical CPR: Continued BLS and ACLS at the scene with manual or mechanical CPR until ROSC is achieved or resuscitation efforts are terminated (current practice).

Risks of ECPR (standard care procedure in hospital): vascular injury, limb ischemia, major hemorrhage, venous thromboembolism, stroke, renal failure, and infection.

Alternatives to ECPR for refractory cardiac arrest: An option is to transport patients to the interventional cardiology laboratory with ongoing CPR for coronary angiography and PCI if indicated. The rationale for this approach is that an acute coronary occlusion is the cause of the cardiac arrest and treating that occlusion could result in ROSC. At this time there is less evidence to support this approach compared to ED-initiated ECPR followed by coronary angiography and PCI following initiation of ECPR if indicated.

Risks of research: improper disclosure or release of personal or medical information.

2.3.2 KNOWN POTENTIAL BENEFITS

The potential benefit of the research to the research subjects is an improved chance of survival with good neurologic function. The current practice for patients with refractory OHCA is for EMS providers to cease resuscitation efforts in the field and pronounce the patients dead. Early transport to an ED capable of advanced resuscitation strategies and ECPR has been reported to result in 4-33% survival with good neurologic function. The potential benefit to society is an improved system of care of OHCA that could double overall survival rates and with widespread implementation save thousands of lives each year in the United States. Reported risks for ECPR include hemorrhage, renal replacement therapy for acute kidney injury, vascular damage, thromboembolism, stroke, and infection. Relative to the potential benefit of survival with good neurologic function, these risks seem reasonable.

3 OBJECTIVES AND PURPOSE

Co-Primary: To determine what proportion of patients with refractory OHCA can be delivered to an ECPR-capable ED within 30 min of the 911 call or prehospital provider witnessed first cardiac arrest (qualifying OHCA event). This is to establish the feasibility of the early transport protocol.

Co-Primary: To determine what proportion of patients can have ECPR initiated within 30 minutes of ED arrival for patients with ongoing refractory OHCA. This is to establish the feasibility of the ED advanced resuscitation protocol in situations where prenotification of the team has occurred by qualified prehospital providers.

Safety: To estimate frequency of adverse events associated with study interventions. This early phase trial is not adequately sized to provide meaningful comparative estimates. The

population of OHCA survivors is at high risk for death and adverse experiences under routine clinical care.

Exploratory: Demonstrate the feasibility of field randomization of patients with refractory OHCA. This study is using a novel procedure to determine eligibility based on timing and location.

Exploratory: We will collect ECPR process measures including time to confirmed vascular access and confirmed ECPR cannulation. These measures are collected as part of routine clinical care on all patients undergoing ECPR for cardiac arrest at the qualified emergency department(s).

Exploratory: To provide preliminary estimates regarding neurological outcomes following this treatment. This study is not adequately sized to provide meaningful comparative data on neurological outcomes. This aim will provide insight into the proportion of patients with excellent outcomes, along with the proportion of patients with neurologically unsatisfactory outcomes.

4 STUDY DESIGN AND ENDPOINTS

4.1 DESCRIPTION OF THE STUDY DESIGN

4.2.1 Primary Endpoints

Co-Primary Endpoint: Time interval from 911 call or prehospital witnessed first cardiac arrest (qualifying OHCA event) to ED arrival in minutes.

The primary endpoint was selected because the goal of the study is to demonstrate the feasibility of transporting patients with refractory OHCA to an ECPR-capable ED within 30 minutes of the 911 call or EMS witnessed arrest.

Co-Primary Endpoint: Time interval from ED arrival to ECPR initiation in minutes

This time interval was chosen because the apparent therapeutic window for OHCA ECPR is 60 minutes and time from ED arrival to ECPR flow is estimated to be 30 minutes.

4.2.2 SAFETY ENDPOINTS

Composite safety endpoint of hemorrhage requiring blood transfusion, pneumothorax requiring thoracostomy, hemopericardium requiring pericardiocentesis.

Composite safety endpoint of, hemorrhage requiring blood transfusion (greater than 4 units packed red blood cells per incident), vessel damage requiring vascular procedure or leading to occlusion, venous/arterial thromboembolism, stroke, renal failure and infection

4.2.3 EXPLORATORY ENDPOINTS

Additional safety outcomes: Splenic injury, liver injury, and all individual components of the composite endpoints listed in 4.2.2

All participants: Utility weighted modified Rankin Scale and cerebral performance category at hospital discharge and 90 days.

Randomization feasibility: Number of attempted uses of randomization app versus successful enrollments

Patient reported outcomes: Neuro-QOL

Cognitive functioning outcomes: NIH-Toolbox

5 STUDY ENROLLMENT AND WITHDRAWAL

5.1 INCLUSION CRITERIA

All adult out-of-hospital cardiac arrest patients, receiving emergency treatment by local Fire Department First Responders capable of using mechanical chest compression devices and Huron Valley Ambulance (HVA) paramedics will be evaluated for this study. This may include ethnic minorities, disabled, and economically challenged populations.

5.1.1 PATIENT LEVEL INCLUSION

- Present with out-of-hospital cardiac arrest, presumed non-traumatic etiology, requiring CPR
- Age presumed or known to be 18 through 70 years old (prior to 71st birthday)
- Predicted arrival time at ECPR-capable hospital within timeframe specified
- Initial shockable rhythm (ventricular tachycardia or ventricular fibrillation) or witnessed pulseless electrical activity or asystole
- Persistent cardiac arrest after initial cardiac rhythm analysis and shock (if shock is indicated)

Participants will be enrolled in the study if they meet initial inclusion criteria at the time of their cardiac arrest.

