10.4.2 ANALYSIS OF THE PRIMARY EFFICACY ENDPOINT(S)

Co-Primary Endpoint(s): Arrival to qualified ED within 30 minutes

The proportion of qualifying episodes to arrive at the ED within 30 minutes will be compared to our historical data point estimate of 38.7% using a one sample exact test of binomial proportions at the 0.05 two-sided significance level.

Co-Primary Endpoint(s): Initiation of ECPR within 30 minutes of ED arrival

Using the modified intention to treat population with ongoing cardiac arrest in the qualified ED, we will declare the analysis of this objective successful if 80% or more of patients have ECPR (qualifying ED standard care process) initiated within 30 minutes of ED arrival. No formal hypothesis test will be conducted.

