 - d. Clinical trials are needed. No prospective, randomized clinical trial has compared standard CPR to ECPR. Almost all published case series of successful ECPR from OHCA initiate ECPR in the emergency department [Chen 2008, Kagawa 2010, Nagao 2000 and 2010, LeGuen 2011, Morimura 2011, Avali 2012, Bellezzo 2012, Johnson 2014, Sakamoto 2014, Stub 2014]. The reason for this strategy is that the shorter the interval from cardiac arrest onset to initiation of ECPR is. The better the chance for a favorable outcome. Scientific evaluation is necessary in order to further test the efficacy of the proposed intervention, transport to an ED for higher level of care and ECPR.
2. Obtaining informed consent is not feasible because:
 - a. Patients who are in cardiac arrest are unresponsive and unable to communicate. It is unreasonable and impractical for first responders to identify, verify, and obtain consent from a legally authorized representative.
 - b. The optimal therapeutic window for initiating interventions and ECPR is within 60 minutes of the cardiac arrest onset.

- c. OHCA patients cannot be identified prospectively
3. Participation in the research holds out the prospect of direct benefit to the subjects because:
- a. Patients are in a life-threatening situation
 - b. Published case series where initiating ECPR in the emergency department have reported survival rates with good neurologic function ranging from 4-33%
 - c. Potential risk of complications of transport with mechanical CPR (rib fractures, pneumothorax, internal organ laceration or motor vehicle crash) or ED initiated ECPR (hemorrhage, vascular injury, deep venous thrombosis, pulmonary embolism, stroke, limb ischemia, infection) are balanced by the anticipated benefit of survival with good neurologic function.
4. The clinical investigation could not be practicably be carried out without the waiver

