APPENDIX B: UMHS ED ECPR GUIDELINES

Extracorporeal cardiopulmonary resuscitation (ECPR) is standard practice in the University of Michigan Hospital Emergency Department. ECPR utilizes a venous-arterial extracorporeal membrane oxygenation (VA-ECMO) circuit built from several components including. These 510K cleared devices may change based on the institutional practice of the hospital and are provided here as an example of the types of devices used.

QUADROX-iD Adult diffusion membrane Oxygenator
CentriMag Primary Console
CentriMag Back-up Console
CentriMag Motor
CardioHelp System

Inclusion/Exclusion criteria for ECPR

Inclusion Criteria:

- Age 18-70
- -Initial shockable (ventricular tachycardia or ventricular fibrillation) or witnessed pulseless electrical activity or witnessed asystole
- Anticipated interval from cardiac arrest onset (or 911 call) to establishing ECMO flow \leq 60 minutes
- Potentially reversible cause of cardiac arrest ¹

Exclusion Criteria:

[figure not shown]
- Sustained return of spontaneous circulation (ROSC)
- DNAR or DNI advanced directive
- Goals of care exclude ECPR (DNAR/DNI, advanced directive, or family discussion)
- Contraindication to anticoagulation ²
- Estimated BMI >40
- Advanced or life-limiting comorbidity ³
- Unable to independently perform ADLs at baseline
- Treating physician and/or ECMO consultant feels that ECPR is futile ⁴

(1) Potentially reversible causes of cardiac arrest include: ACS, refractory arrhythmia, myocarditis, massive PE, severe hypothermia, drug overdose

(2) Contraindications to anticoagulation include: Suspected or known intracranial hemorrhage, traumatic arrest, significant active bleeding

- (3) Advanced or life-limiting co-morbidities include: Stroke or CNS lesion with significant neurologic or cognitive impairment, liver cirrhosis including ESLD, ESRD, advanced COPD or other chronic lung disease, advanced or metastatic malignancy
- (4) Indications of futility are subject to the gestalt of the treating physician and/or ECMO surgeon, but may include: Septic shock multiorgan failure, hypoxemic arrest, metabolic acidosis with pH <7.0, Lactate >15, ETCO₂ <10 despite optimal ACLS, poor candidate for destination LVAD, artificial heart, or transplant

UMHS AES ECPR Protocol

- (1) Inclusion/Exclusion criteria per Appendix 1

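### Field criteria admit patients whom Appendix B would decline for ECPR, and 10.3 and 10.4.2 disagree on whether they count in the 80% co-primary

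*Combined protocol and SAP*

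**What the plan says.** **Who is enrolled.** Section 5.1.1 requires presumed non-traumatic arrest, age 18 through 70, a predicted arrival time in the window, persistent arrest, and "Initial shockable rhythm (ventricular tachycardia or ventricular fibrillation) or witnessed pulseless electrical activity or asystole". Section 5.2 excludes sustained ROSC, DNAR/DNI, opt-out, prisoners, pregnancy, a destination without ECPR, and refusal at the scene.

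**Whom the ED would cannulate.** Appendix B shares the age range, the ROSC exclusion and the DNAR/DNI exclusion. Its rhythm line repeats the qualifier: "or witnessed pulseless electrical activity or witnessed asystole". It also requires a potentially reversible cause. It excludes a contraindication to anticoagulation, an estimated BMI above 40, "Advanced or life-limiting comorbidity" (ESRD, cirrhosis, advanced COPD and advanced malignancy are among the examples), "Unable to independently perform ADLs at baseline", and futility as judged by the treating physician or ECMO consultant. None of these is in 5.1.1 or 5.2.

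**Who is counted in the ECPR co-primary.** Three places give three populations:
- Section 2.2 states the 30-minute goal as "arrival to cannulation for all patients meeting inclusion/exclusion criteria for ECPR therapy".
- Section 10.3, under a modified per-protocol label, takes early-transport patients still in arrest at least 10 minutes after ED arrival in whom the institutional ECPR process was initiated.
- Section 10.4.2 declares success at 80% or more, "Using the modified intention to treat population with ongoing cardiac arrest in the qualified ED", with no 10-minute condition and no formal test.

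Section 7.3.2 foresees randomized patients who do not receive ECPR and follows them, but does not say how they enter this endpoint.

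**The concern.** The second co-primary is meant to show that the ED can start ECPR within 30 minutes of arrival. A patient properly declined under the ED's guideline says nothing about speed. An eligible patient in whom ECPR was never started says a great deal. Neither 10.3 nor 10.4.2 separates the two: 10.4.2 counts both as failures and 10.3 removes both. As the success rule is a bare 80% threshold applied to at most about two dozen patients, a handful of such cases can decide the outcome, and the analyst would be choosing the denominator with the data in view.

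There is a related disclosure point. Section 13.1 supports the prospect of direct benefit partly with this: "Published case series where initiating ECPR in the emergency department have reported survival rates with good neurologic function ranging from 4-33" per cent. Those series describe patients in whom ECPR was started, and some people enrolled here without consent will not be candidates for it.

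**Working it through.** **1. The plan's own figure.** The only power statement (Section 10.5) concerns ED arrival: n = 24, 38.7% against 19/24 = 79.2%, 98%. The exact two-sided test rejects at 15/24 or more (upper tail 0.0156), and power at 79.2% is 98.3%, so the figure reproduces. ECPR eligibility does not affect it. No operating characteristics are given for the ECPR endpoint.

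**2. Inputs.** From the documents: the 80% threshold (10.4.2), and 30 patients at 4:1, hence 24 in early transport (10.5, 10.6.1). Assumed, because the documents do not give them: the ineligible share f among patients in arrest at the ED (0 to 30%), the on-time rate s among eligible patients (90%), and the number in arrest at the ED, N (24, 18 or 12). N = 24 is a ceiling, since some patients will regain circulation before or after arrival.

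**3. How many ineligible patients 10.4.2 tolerates.** The number of successes needed is 0.80N rounded up.
- N = 24: 0.80 × 24 = 19.2, so 20 needed and 4 non-starts tolerated. With 5 ineligible and all others on time, 19/24 = 79.2%, which fails.
- N = 18: 14.4, so 15 needed and 3 tolerated.
- N = 12: 9.6, so 10 needed and 2 tolerated.

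For the expected rate to reach 80%, s must be at least 0.80/(1 − f): 88.9% at f = 10%, 94.1% at 15%, 100% at 20%.

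**4. Chance of declaring success with s = 90%.** Under 10.4.2, successes are Binomial(N, (1 − f)s). Under 10.3, the number analysed M is Binomial(N, 1 − f), successes are Binomial(M, s), and 0.80M rounded up are needed. The 10.3 column assumes that the process is started in every eligible patient.

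| f | N=24: 10.4.2 / 10.3 | N=18: 10.4.2 / 10.3 | N=12: 10.4.2 / 10.3 |
|---|---|---|---|
| 0% | 0.915 / 0.915 | 0.902 / 0.902 | 0.889 / 0.889 |
| 10% | 0.510 / 0.934 | 0.545 / 0.917 | 0.594 / 0.895 |
| 20% | 0.156 / 0.923 | 0.214 / 0.899 | 0.304 / 0.866 |
| 30% | 0.027 / 0.912 | 0.056 / 0.885 | 0.120 / 0.845 |

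Under 10.3 the expected rate stays at 90%. Only the number analysed falls, and the small movements reflect rounding of the threshold.

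**5. The opposite error under 10.3.** Take, for illustration only, 24 in arrest: 5 ineligible, 3 eligible but never started, 16 started, 14 of them on time.
- Section 10.3: 14/16 = 87.5%, success.
- Section 10.4.2: 14/24 = 58.3%, failure.
- Eligible patients, as in the 2.2 goal: 14/(24 − 5) = 14/19 = 73.7%, failure.

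If instead all 19 eligible patients are started on time, 10.4.2 gives 19/24 = 79.2% (failure) while the other two give 19/19. So 10.4.2 can fail a service that treated every candidate in time, and 10.3 can pass one that left candidates untreated.

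**The case against.** Three stronger readings are tempting, and the documents do not support them.

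- *Ineligible patients are scored as failures of ECPR speed.* This follows from 10.4.2 alone. Section 10.3, which defines the analysis sets, on its natural reading removes anyone in whom the process was not initiated. The losses in step 4 belong to the 10.4.2 denominator only.
- *These patients are transported toward a therapy they cannot get.* Section 6 offers the appendices as examples of local guidelines, futility is a case-by-case judgement, and Section 2.3.2 bases benefit on advanced resuscitation as well as ECPR. What can be said is that the receiving ED's guideline would decline them. The example status does not remove the point: there is one site, one listed hospital, and Appendix B is that hospital's guideline.
- *Section 5.1.1 admits unwitnessed asystole.* The word witnessed may govern both rhythms, which would match Appendix B. The omissions relative to Appendix B are the stronger evidence.

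It can also be argued that broad field criteria are intended. The dispatcher enters only address, age and call time (7.3.1), and pH, lactate and often comorbidity are unknowable on scene. That is a fair reason not to align the lists fully, but the plan does not state it, and it leaves the denominator unsettled.

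Finally, restricting the endpoint to eligible patients carries a risk of its own. In an open-label study, a slow case could be relabelled futile afterwards. That objection stands, and the fix has to guard against it.

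**Conclusion.** The eligibility gap is real and verifiable from the text. Its statistical consequence is an unresolved denominator: 10.3 and 10.4.2 conflict, and neither matches the 2.2 goal. The choice can decide the co-primary. With 24 in arrest, five ineligible patients rule out success under 10.4.2 and leave the 10.3 rate untouched. At an assumed 20% ineligible and 90% on time, the chance of success is 0.16 against about 0.92. The ineligible share, the on-time rate and the number in arrest are assumptions, but the dependence on the denominator is not. The ED-arrival co-primary and its 98% power are unaffected. The documents do not show that the plan as a whole scores declined patients as failures.

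**What to change.** 1. Use one denominator in 10.3 and 10.4.2, consistent with 2.2: early-transport patients still in arrest at the qualified ED who meet the ECPR criteria. Count eligible patients never started as failures. Keep or drop the 10-minute condition in both sections, and use one label for the population.
2. For each early-transport patient in arrest at the ED, record which Appendix B criterion was met or failed, from the ED record and as documented when the decision was made. List patients declined for futility separately, and report the all-in-arrest proportion beside the primary result.
3. Reconcile the 5.1.1 rhythm and witness line and the 5.2 exclusions with Appendix B, or state that the broader field criteria are intended. Which clinical criterion should apply is for the investigators to decide.
4. Acknowledge in 13.1 that some enrolled patients will not be ECPR candidates.

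The cost is protocol wording and a CRF field; Section 7.3.2 already abstracts physician notes, comorbidities and ECPR status. The ECPR denominator becomes smaller than all patients in arrest and rests partly on a clinical judgement, which the all-in-arrest proportion and the separate futility list make visible.
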